5.2 Inclusion Criteria

Women must meet all of the following criteria to be eligible for inclusion in the study. Any exclusionary laboratory values can be repeated at a later date within the Screening window. If the repeated laboratory values meet inclusion criteria then the participant can be enrolled. If there is concern that the participant's health status has changed between the screening visit and the enrollment visit or if there is a clinical concern by the study investigators, the screening laboratories can be repeated prior to enrollment.

- 1) Age 18 through 39 years (inclusive) at Screening
- 2) Able and willing to provide written informed consent and take part in the study procedures
- 3) Able and willing to provide adequate locator information
- 4) Chronic HCV (for at least 6 months prior to screening) by participant report
- 5) Detectable HCV RNA viral load at Screening
- 6) Desired pregnancy at 23 + 0 to 25 + 6 weeks' gestation at Enrollment with gestational dating confirmed by ultrasound
- 7) Singleton gestation with no known fetal abnormalities
- 8) Documented negative Hepatitis B testing for current infection (negative HBsAg test) or previous infection (negative anti-HB Core) performed at the screening visit
- 9) Negative HIV testing at the screening visit

- 10) Per participant report at Screening and Enrollment, agrees not to participate in other research studies involving investigational drugs or medical devices for the duration of study participation

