5.3 Exclusion Criteria

Women who meet any of the following criteria will be excluded from the study:

- 1) Participant report of any of the following at Screening or Enrollment:
 - a. Previous treatment for Hepatitis C virus with sofosbuvir or a NS5A inhibitor
 - b. Use of any medications contraindicated with concurrent use of velpatasvir or sofosbuvir according to the most current EPCLUS³⁴ package insert³⁴
 - c. Plans to relocate away from the study site area in the next 1 year and 4 months and unable/unwilling to return for study visits
 - d. Current sexual partner is known to be infected with HIV or Hepatitis B virus
 - e. History of cirrhosis documented or reported by previous liver biopsy or liver imaging tests
- 2) Reports participating in any other research study involving investigational drugs or medical devices within 60 days or less prior to Enrollment
- 3) Clinically significant and habitual non-therapeutic drug abuse, not including marijuana, as determined by Protocol Chair
- 4) At Screening or Enrollment, as determined by the Protocol Chair, any significant uncontrolled active or chronic cardiovascular, renal, liver (such as evidence of decompensated cirrhosis by ascites, encephalopathy, or variceal hemorrhage), hematologic, neurologic, gastrointestinal, psychiatric, endocrine, respiratory, immunologic disorder or infectious disease (other than Hepatitis C)
- 5) Has a high risk of preterm birth defined as a history of spontaneous preterm birth at less than 34 weeks of gestation or a shortened cervical length of less than 20 millimeters
- 6) Has any of the following laboratory abnormalities at Screening:
 - a. Aspartate aminotransferase (AST) or alanine transaminase (ALT) greater than 10 times the upper limit of normal
 - b. Hemoglobin less than 9 g/dL
 - c. Platelet count less than 90,000 per mm³
 - d. International normalized ratio (INR) > 1.5

- e. Creatinine greater than 1.4
- 7) Has any other condition that, in the opinion of the IoR/designee, would preclude informed consent, make study participation unsafe, complicate interpretation of study outcome data, or otherwise interfere with achieving study objectives.

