10.2.2 Secondary Endpoints: Maternal

The secondary endpoints of the study are:

- 1) Secondary plasma PK endpoints of VEL, SOF and GS-331007:
 - a. Free-fraction of VEL, SOF and GS-331007
- 2) Secondary PK endpoints for intracellular SOF (GS-461203)
 - a. Pre-dose GS-461203 concentrations from dried blood spots and peripheral blood mononuclear cells
- 3) Maternal sustained virologic response after 12 weeks of therapy (SVR12)
- 4) Adverse events including clinical and laboratory changes
- 5) Pregnancy outcomes including the following:
 - a. delivery prior to 37 completed weeks of gestation
 - b. stillbirth or intrauterine fetal demise
 - c. intrapartum hemorrhage
 - d. postpartum hemorrhage
 - e. non-reassuring fetal status
 - f. chorioamnionitis
 - g. hypertensive disorders of pregnancy
 - h. gestational diabetes
 - i. intrauterine growth restriction

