10.3 Sample Size

To evaluate the primary objective, we estimate a desired sample size of 10 participants. In order to maintain our sample size, any participant who discontinues treatment during the 12-week treatment period will be replaced. Based on SOF/VEL prescribing information, we will have 87% power to detect a 50% decrease in VEL AUC and >99% power to detect a 2-fold increase. For power calculations we chose this degree of change in VEL AUC because the therapeutic range of SOF/VEL is quite wide and decreases in VEL AUC of up to 50% and increases of up to 2-fold are still associated with efficacy and have acceptable safety/tolerability, respectively.

The FDA does not recommend co-administration of VEL with EFV because it decreases the VEL AUC by >50% [34]. Additionally, this sample size provides an estimated power of 0.82 to detect a 25% change in the AUC of the SOF, given the reported interpatient variability of 35.6% among female patients. Power determinations were performed in SAS v. 9.4 (SAS, Cary, NC).

Any participant that discontinues the study before the PK3 visit is completed or if a participant reports missing more than 1 dose per week averaged over the duration of the study then they will be replaced by recruiting another participant into the study.

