10.5.3 Analysis of Safety Endpoints

Rates of abnormal safety laboratory assessments will be compared to those reported in the literature on historic controls and rates of adverse pregnancy outcomes will be compared to historic HCV-infected pregnant women who have delivered at our institution. Statistical significance will be determined by chi-square test.

Qualitative Analysis

Following transcription of the IDIs, the Qual EASE team will develop a qualitative codebook using an editing approach to ensure that all relevant topics and themes are represented. Two trained qualitative coders from Qual EASE will then be trained in the codebook. A primary coder will code all interviews in the pre- and post-treatment interview groups, and a secondary coder will code half of the interviews in the pre- and post-treatment interview groups. Coding will be completed using Atlas.ti software, which will help to determine the frequency and prevalence of the topics and themes which were discussed. Cohen's Kappa scores will be calculated to determine intercoder reliability.

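### The historic comparison group for pregnancy outcomes is not aligned with the trial's eligibility criteria, so the benchmark, above all for preterm delivery, is expected to be too high

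*Combined protocol and SAP*

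**What the plan says.** Under 10.5.3 (Analysis of Safety Endpoints), "rates of adverse pregnancy outcomes will be compared to historic HCV-infected pregnant women who have delivered at our institution", and "Statistical significance will be determined by chi-square test". The section gives no calendar years, cohort size, inclusion rule, gestational age at which follow-up starts, matching or adjustment. The pharmacokinetic historical controls in 10.5.1, by contrast, are restricted to nonpregnant women without severe renal disease or cirrhosis.

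Entry to the trial is narrower. Section 5.2 requires "Desired pregnancy at 23 + 0 to 25 + 6 weeks" of gestation at enrolment and "Singleton gestation with no known fetal abnormalities". Section 5.3 excludes a woman who "Has a high risk of preterm birth defined as a history of spontaneous preterm birth at less than 34 weeks of gestation" or a cervical length below 20 mm. It also excludes significant uncontrolled disease and habitual non-therapeutic drug abuse other than marijuana.

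Section 10.2.2 lists nine pregnancy outcomes. The first is "delivery prior to 37 completed weeks of gestation" and the second is stillbirth or fetal demise. On size, 10.3 says "we estimate a desired sample size of 10 participants".

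**The concern.** The trial screens out women whom the protocol itself labels as being at high risk of preterm birth, and then measures preterm birth. It also begins observation only once a pregnancy has reached 23 weeks. If the historic group is not filtered in the same way, its rate describes a higher-risk population, and treated women would be expected to do better even if the drug had no effect.

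This is the only planned comparison of pregnancy outcomes. Section 13.3.1 states that there are no studies of SOF/VEL in pregnant women, and section 2.5 places this trial ahead of larger treatment studies. A falsely reassuring benchmark could be carried into that later work. An exact test or an exact interval would deal with the small numbers but not with a mismatched benchmark.

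**Working it through.** The plan states no historic rate, error level or power for this comparison, so there is no figure of its own to reproduce. The rates, excluded shares, relative risks, historic group sizes and two-sided 0.05 level below are assumptions for illustration. The 10 women and the eligibility criteria come from the documents.

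**1. Which outcomes the criteria act on.**

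- Delivery before 37 weeks: affected directly, through prior preterm birth, short cervix, singleton status and being undelivered at 23 weeks.
- Stillbirth or fetal demise: affected in part, through singleton status, absence of known abnormality and a live pregnancy at enrolment. No enrolled woman can have a loss before 23+0. Such losses distort the comparison only if the historic group counts them, which the plan does not say.
- Haemorrhage, chorioamnionitis, hypertensive disorders of pregnancy, gestational diabetes and growth restriction: no criterion screens for any of these by name.

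**2. Inflation of the preterm benchmark.** Let e be the rate in eligible women, q the share of historic women the trial would exclude, and RR their risk relative to eligible women. Then

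unrestricted rate = e × (1 − q + q × RR).

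With e = 15%:

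| q | RR | Unrestricted rate | Ratio to 15% |
|---|---|---|---|
| 5% | 2 | 15.75% | 1.05 |
| 10% | 2 | 16.5% | 1.10 |
| 10% | 3 | 18.0% | 1.20 |
| 15% | 3 | 19.5% | 1.30 |

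The apparent risk ratio for an inert drug is the reciprocal: 1/1.05 = 0.95 down to 1/1.30 = 0.77. A wider assumption, q = 30% with RR = 3, gives 1/(0.7 + 0.9) = 0.63.

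**3. Scale against 10 women.** The gap in expected events is 10 × (0.1575 − 0.15) = 0.08 up to 10 × (0.195 − 0.15) = 0.45.

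**4. Can the test show a significant benefit?** I used uncorrected chi-square with historic groups of 100, 369 and 1000. (369 is the size of an institutional cohort of HCV-seropositive women mentioned in 2.2; the plan does not say that it is the comparator.) For historic rates from 15% to 19.5%, even 0 events in 10 gives p = 0.12 to 0.19, so it cannot. At a 30% historic rate and 369 controls, 0 of 10 would give p = 0.04.

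**5. Can the mismatch hide harm?** Take 369 historic women and 4 preterm deliveries among the 10.

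- Aligned benchmark of 15% (55 of 369): pooled rate 59/379 = 0.156; chi-square = (0.400 − 0.149)² / [0.156 × 0.844 × (1/10 + 1/369)] = 4.7; p = 0.03.
- Unrestricted benchmark of 18% (66 of 369): pooled rate 70/379 = 0.185; chi-square = (0.400 − 0.179)² / [0.185 × 0.815 × (1/10 + 1/369)] = 3.2; p = 0.08.

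The threshold for a harm signal moves from 4 events to 5. If SOF/VEL truly doubled the risk to 30%, the chance of reaching it is P(X ≥ 4) = 35% against the aligned benchmark and P(X ≥ 5) = 15% against the inflated one, with X binomial (10, 0.30). The shift does not occur in every case: with 369 controls it needs an unrestricted rate of about 16.5% or more, and at 15.75% the threshold stays at 4.

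**The case against.** The strongest reply is that 10.5.3 leaves the comparator undefined. A reader might infer that it will contain all historic HCV-infected deliveries, multiples and anomalies included. The text does not say so; this is read from the absence of any restriction, and the analysts might filter sensibly in practice. That stands as a limit on wording. It does not remove the point, because a plan followed as written applies no filter.

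A reader might also infer that SOF/VEL is bound to look safer. The documents do not support that certainty. Section 5.1.1 directs recruitment mainly to an opioid-dependence prenatal programme, whose case mix may differ from historic deliveries in either direction. Trial outcomes are collected prospectively by interview and record review, which may capture more events than old records. The direction is expected, not established.

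Third, sample size is the larger limit. Even with a perfect benchmark the test misses a true doubling about two times in three (1 − 0.35 = 0.65), and 0 events in 10 still has an upper 95% limit of 1 − 0.025^(1/10) = 31%. That is correct, but imprecision is no reason to accept an avoidable bias as well.

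Finally, safety oversight does not depend on this test. Two independent physicians, an obstetrician and a pediatrician, review data about monthly, and a pause or stop can be recommended (8.1, 8.2, 10.5.4). Any masking of harm is therefore confined to this secondary comparison.

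**Conclusion.** The point holds as a mismatch between an unrestricted historic group and a selected trial group. It is clearest for delivery before 37 weeks, and extends to fetal loss if losses before 23 weeks are counted. For most of the other listed outcomes the documents show no direct filter, so a claim that the whole set of pregnancy outcomes is biased would go too far.

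The size cannot be established from the documents. Under the assumptions shown, the preterm benchmark is inflated by 5% to 30%, which is less than half an expected event in 10 women. It would not produce a statistically significant benefit in that range. It can cut the chance of flagging a true doubling from 35% to 15%. Confidence is high in the mismatch, moderate in its direction and low in its magnitude. This is a cheap improvement to a secondary analysis, not a flaw in the primary pharmacokinetic objective.

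**What to change.** In 10.5.3, define the historic cohort before outcomes are examined. As far as records allow, restrict it to women who would have met the trial's eligibility criteria: at least age 18 to 39, singleton, no fetal abnormality known by enrolment gestation, no spontaneous preterm birth before 34 weeks, and no recorded cervical length under 20 mm. Require that they were undelivered with a live fetus at 23+0 weeks, and count outcomes from 23+0 onward. Use that rate as the benchmark and show the unrestricted rate only for context. State which criteria could not be applied.

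The cost is a short addition to 10.5.3 and some filtering of institutional obstetric records; treatment, visits and sample size do not change. Section 8.2 already mentions extraction from institutional databases, though for trial participants, so access to the historic data needs confirming. The drawbacks are a smaller historic cohort and incomplete recording of items such as cervical length and drug use. A small residue remains: a woman enrolled at 25+6 has already passed 20 days beyond 23+0 without delivering.

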 - HCV RNA viral load will be assessed at 12 weeks after completion of SOF/VEL treatment. An undetectable viral load will be considered a SVR12.

- **Maternal Safety**
 - Safety laboratory assessments of blood counts, creatinine, liver function, creatinine kinase and lipase will be measured at the PK1 and PK2 visits (approximately 3 weeks and 6 weeks after treatment initiation).
 - Pregnancy and delivery outcomes collected prospectively by participant interview and medical record review.
- **Neonate Safety**
 - Major malformations, defined as structural abnormalities with medical, surgical or cosmetic importance;
 - Weight, length, and head circumference at birth, 8 weeks, 6 months and 12 months;
 - HCV RNA viral load at birth (as available), 1 to 3 months, at 6 months and then again at 12 months only if negative viral loads are not documented at 1 to 3 and 6 months;
 - Neurodevelopmental assessments at 6 months and 12 months.

Exploratory Objectives:

- Describe the perspectives of pregnant women with chronic HCV infection screening for a trial of antenatal sofosbuvir/velpatasvir (SOF/VEL) therapy

Exploratory Endpoint:

- In depth interviews conducted before enrollment in screened participants and after completion of treatment in enrolled participants.

Table 1: Study Visit Schedule

	Maternal Study Visit	Target windows [†]
V1	Screening	14+0 to 22+6 weeks gestation (weeks + days)
V2*	Enrollment	23+0 to 25+6 weeks gestation (weeks + days)
V3	PK1: Intensive	3 weeks \pm 7 days after first dose of SOF/VEL
V3a [^]	PK1a, 24hr sample	24 hours \pm 2 hours
V4	PK2: Sparse	6 weeks \pm 7 days after first dose of SOF/VEL
V5	PK3: Intensive	9 weeks \pm 7 days after first dose of SOF/VEL
V5a [^]	PK3a, 24hr sample	24 hours \pm 2 hours
V6	End of Treatment	Within 7 days of SOF/VEL completion
Del**	Delivery	
V7/iV1	Post treatment	12 weeks \pm 4 days after completion of therapy
	Infant Study Visit	Infant Age
Del**	Delivery	Newborn
V7/iV1	Infant Visit 1	8 weeks \pm 6 weeks [†]
iV2	Infant Visit 2	6 months \pm 2 weeks [†]
iV3	Infant Visit 3	12 months \pm 2 weeks [†]

[†]These are target windows. If the participant cannot be seen within these windows then it will not be considered a protocol deviation.

*Start SOF/VEL and continue for 12 weeks

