2.2 Rationale

Pregnancy is a critical window of opportunity for HCV screening and treatment. Pregnancy may be the ideal time to provide HCV treatment due to enhanced maternal investment in neonatal health outcomes. A meta-analysis of adherence to antiretroviral therapy during and after pregnancy showed a statistically significant difference in adherence during pregnancy (75.5%) compared to the postpartum period (53.0%)²³. In a retrospective cohort study of 369 pregnant women who were HCV seropositive at our institution from 2009 to 2012, 285 (77%) were referred to hepatology for postpartum treatment, but only 71 (25%) attended the consultation and only 6 (1.6%) were treated in the first year postpartum²⁴. Furthermore, in an ongoing study of postpartum HCV treatment with SOF/VEL paired with medication-assisted treatment (MAT) at our institution, 6 (50%) of 12 enrolled participants were lost to follow-up prior to treatment completion²⁵. *Thus, pregnancy may be the ideal period for enhanced HCV treatment adherence and engagement.*

Addressing the knowledge gap: pharmacokinetic and safety studies of new antivirals in pregnancy. Significant physiologic changes occur during pregnancy that effect drug absorption, distribution, metabolism and excretion, resulting in PK changes which may have clinical consequences²⁶. For example, increased renal clearance of drugs could result in suboptimal concentrations with standard dosing for renally cleared drugs, leading to antiviral resistance or decreased efficacy²⁷. To illustrate this, some antiretroviral medications, such as atazanavir and lopinavir, require dose changes during pregnancy to achieve therapeutic drug concentrations in the late second or third trimesters²⁷. Plasma protein concentrations including alpha-1 acid glycoprotein and albumin decrease in pregnancy, potentially influencing free drug concentrations; therefore, to comprehensively evaluate the impact of these physiologic changes in pregnancy for highly protein bound drugs, assessment of both total and free drug concentrations is critical.

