Hepatitis B virus (HBV) reactivation has been reported in HCV/HBV coinfecting patients who were undergoing or had completed treatment with HCV direct acting antivirals, and who were not receiving HBV antiviral therapy. Some cases have resulted in fulminant hepatitis, hepatic failure, and death. Cases have been reported in patients who are HBsAg positive and also in patients with serologic evidence of resolved HBV infection (i.e., HBsAg negative and anti-HBc positive). We will exclude participants that are anti-HBc positive for this reason. Additionally, postmarketing cases of symptomatic bradycardia and cases requiring pacemaker intervention have been reported when amiodarone is coadministered with a sofosbuvir-containing regimen. Additionally a fatal cardiac arrest occurred in a patient taking amiodarone that was co-administered with sofosbuvir. For this reason, we will exclude participants who are taking amiodarone³⁴.

Laboratory abnormalities:

Lipase Elevations: In ASTRAL-1, isolated, asymptomatic lipase elevations of greater than 3 times the upper limit of normal were observed in 3% and 1% of participants treated with SOF/VEL and placebo for 12 weeks, respectively; and in 6% and 3% of participants treated with SOF/VEL in ASTRAL-2 and ASTRAL-3, respectively³⁴.

Creatine Kinase: In ASTRAL-1, isolated, asymptomatic creatine kinase elevations greater than or equal to 10 times the upper limit of normal were reported in 1% and 0% of participants treated with SOF/VEL and placebo for 12 weeks, respectively; and in 2% and 1% of participants treated with SOF/VEL in ASTRAL-2 and ASTRAL-3, respectively.

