5.1.1 Recruitment

There are over 10,000 deliveries at Magee-Womens Hospital (MWH) per year and it is estimated that approximately 1% of women who deliver are actively infected with HCV. HCV-infected pregnant women will be recruited from MWH and antenatal clinics, opiate substitution therapy clinics and recovery programs in Pittsburgh and surrounding areas.

Recruitment will be primarily targeted from the MWH Pregnancy Recovery Center, which was established in 2014 to provide concurrent treatment for opiate dependence (buprenorphine) with prenatal care, which has an estimated retention rate of 90% for weekly opiate substitution and prenatal visits. There are approximately 120 opiate addicted pregnant women who received prenatal care at the Pregnancy Recovery Center per year. The prevalence of HCV infection in this Center is approximately 60%. Recruitment will also be targeted at the Magee-Womens Hospital ambulatory clinic and associated clinics that deliver at Magee-Womens Hospital. In order to engage HCV-infected women in recovery, but not yet engaged in prenatal care, we may also recruit patients from local opiate substitution therapy clinics and recovery programs that treat pregnant women.

Recruitment may also include women who are not receiving care at Magee-Womens Hospital through referrals from health care providers. These women must be willing to travel to Pittsburgh to complete the study visits but may deliver at an outside hospital as information from delivery may be reviewed after obtaining a signed medical record release.

Recruitment materials will be approved by the University of Pittsburgh Institutional Review Board prior to use.

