5.1.2 Retention

The importance of retention will be stressed to the participant at each visit as part of protocol adherence counseling. Once a participant is enrolled, the study staff will make every effort to retain the participants in follow-up to minimize possible bias associated with loss-to-follow-up. Any participant that discontinues the study before the PK3 visit is completed or reports missing more than 1 dose per week averaged over the duration of the study will be replaced by recruiting another participant into the study. We anticipate needing to replace no more than one participant.

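### Section 10.5.3 rests its two maternal safety comparisons on a chi-square test with only 10 women; for events near 1% the approximation is unreliable, so exact intervals should lead

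*Combined protocol and SAP*

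**What the plan says.** Section 10.5.3 sets up two comparisons for the mothers. Abnormal safety laboratory results are set against literature rates in historic controls, and "rates of adverse pregnancy outcomes will be compared to historic HCV-infected pregnant women who have delivered at our institution". One sentence governs both: "Statistical significance will be determined by chi-square test".

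The planned sample is 10 women (sections 10.1 and 10.3). Neither section 10.5.3 nor any other part of the plan gives, for these tests, an exact alternative, a small-count rule, a choice on continuity correction, an alpha or a sidedness. The only inferential level in the statistical section is the 90% confidence interval for the pharmacokinetic ratios (section 10.5.1).

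The documents do give laboratory rates under SOF/VEL. In section 2.4.1, for ASTRAL-1 (treated, then placebo), "isolated, asymptomatic creatine kinase elevations greater than or equal to 10 times the upper limit of normal were reported in 1% and 0% of participants"; the ASTRAL-2 and ASTRAL-3 figures are 2% and 1%. Lipase elevations above three times the upper limit occurred in 3% of treated participants in ASTRAL-1 and "in 6% and 3% of participants treated with SOF/VEL in ASTRAL-2 and ASTRAL-3, respectively". No rate is given for any pregnancy outcome, and neither control group's size is stated.

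**The concern.** The chi-square p-value is a large-sample approximation, and 10 women do not supply a large sample for uncommon events. Two things follow. First, chi-square can mean the uncorrected Pearson statistic or the Yates-corrected one, and at these counts the two can give opposite answers, so the written rule does not fix the result. Second, the uncorrected version may reject too often when events are rare.

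At stake is the reading of a single rare abnormality. Maternal and neonatal safety is a stated secondary objective, and section 2.5 says there is no prior experience with SOF/VEL in pregnancy. One raised creatine kinase among 10 women could be reported as a significant finding under one option and not under the others. If the method is chosen after the counts are known, the label loses its meaning.

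**Working it through.** The plan states no power, alpha or expected count for these comparisons, so there is no figure to reproduce.

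**Inputs.** From the documents: n = 10 women; laboratory rates of 1%, 2%, 3% and 6% (section 2.4.1). Assumed, because the plan does not say: two-sided 0.05; each woman counted once; control size N. For N, I use 1035 (the three-trial SOF/VEL total in section 2.4.1), 369 (the size of the institutional cohort in section 2.2: "In a retrospective cohort study of 369 pregnant women who were HCV seropositive at our institution from 2009 to 2012") and 200 as a smaller case. Section 10.5.3 does not name either documented group as its comparator.

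**Step 1: expected counts.** Expected treated events = 10 × p, which is 0.1, 0.2, 0.3 and 0.6 at 1%, 2%, 3% and 6%. The two treated cells sum to 10, so both reach 5 only at a pooled rate of exactly 50%. For pregnancy outcomes, at least one treated cell is therefore below 5 at any other rate. How far below cannot be said without rates.

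**Step 2: one event in 10 against a 1% control rate.** With a of n treated events, c of N control events, b = n − a, d = N − c, T = n + N and m = a + c:

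X² = T(ad − bc)² / [n·N·m·(T − m)]

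For 1/10 vs 10/1035: ad − bc = 1025 − 90 = 935, so X² = 1045 × 935² / (10 × 1035 × 11 × 1034) = 7.76 and p = 0.005. The Yates version replaces 935 by 935 − 1045/2 = 412.5, so X² = 1.51 and p = 0.22. Fisher's exact p is 0.10.

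| Controls | Pearson | Yates | Fisher |
|---|---|---|---|
| 2/200 | 0.019 | 0.33 | 0.14 |
| 4/369 | 0.015 | 0.30 | 0.13 |
| 10/1035 | 0.005 | 0.22 | 0.10 |

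With N = 1035, one event stays significant by Pearson up to 17/1035 (1.6%, p = 0.043) and not at 18/1035 (p = 0.052).

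**Step 3: actual type I error at nominal 0.05.** Sum Bin(a; 10, p) × Bin(c; N, p) over every table whose p-value is at most 0.05.

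| True rate | N | Pearson | Fisher |
|---|---|---|---|
| 1% | 369 | 8.0% | 0.65% |
| 1% | 1035 | 9.4% | 0.6% |
| 1.5% | 369 | 7.8% | 1.0% |
| 1.5% | 1035 | 10.2% | 0.9% |
| 3% | 1035 | 3.5% | 2.9% |
| 5% | 369 | 5.7% | 1.7% |
| 5% | 1035 | 7.1% | 1.2% |
| 10% | 369 | 4.8% | 2.0% |
| 15% | 369 | 4.2% | 2.6% |

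With N = 200 the Pearson figures at 1% and 1.5% are 6.6% and 6.5%.

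**Step 4: higher rates.** Against N = 1035 at 2%, 3% and 6%, Pearson, Yates and Fisher agree at every event count from 0 to 10. At rates that pregnancy outcomes might have (assumed, N = 369), Pearson and Fisher can differ: 2/10 vs 18/369, 0.035 and 0.092; 3/10 vs 37/369, 0.043 and 0.078; 4/10 vs 55/369, 0.031 and 0.054. The bands are narrow. A split needs 13 to 19 control events (3.5% to 5.1%) for 2/10, 31 to 38 (8.4% to 10.3%) for 3/10, and 54 to 60 (14.6% to 16.3%) for 4/10.

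**Step 5: what an exact interval shows.** For 0/10 the Clopper-Pearson upper 95% limit is 1 − 0.025^(1/10) = 30.8%. For 1/10 the interval is 0.25% to 44.5%, and for 2/10 it is 2.5% to 55.6%.

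**The case against.** The strongest reply is that alpha is my assumption. At 0.10, Pearson's size for a 1% event is 9.0% to 9.6% (N = 277 to 1035), so it is not inflated there, and the three pregnancy examples no longer split, since every Fisher p is below 0.10. That is correct, and it limits the claim. It does not remove it: at 0.10, 1/10 vs 10/1035 still splits (Fisher 0.101), and Pearson's size at a 1.5% rate is 13.5% with N = 1035.

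A second reply is that 1035 is not the denominator of the 1% creatine kinase rate, which section 2.4.1 gives for ASTRAL-1 and ASTRAL-3 separately. This also stands. The genotype table there gives 277 for ASTRAL-3 (genotype 3) and, for ASTRAL-1, between 520 (genotypes 1, 4, 5 and 6: 328 + 116 + 35 + 41) and 758 (adding all 238 with genotype 2). One event then gives a Pearson p of 0.007 to 0.018 and a type I error at 1% of 8.2% to 9.2%. The direction is unchanged. The plan also does not adopt that creatine kinase cut-off, and its panel is wider.

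Two stronger readings are tempting. A reader might infer that every safety comparison in the trial is affected, with expected counts far below 5 throughout. The documents support this only for the two maternal comparisons, and the very small counts only for the quoted laboratory rates; no test is named for infant outcomes. A reader might also infer that chi-square inflates false positives generally. Steps 3 and 4 show that it does not.

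**Conclusion.** The point holds in a limited form. The stated rule is a poor approximation for rare laboratory events in 10 women, and it leaves the result open between two versions of the same test. At two-sided 0.05, one event against a 1% control rate is significant by uncorrected chi-square and clearly not by Yates or Fisher, for every control size tried from 200 to 1035. The uncorrected test's type I error is about 8% to 10% at 1% to 1.5% with 369 to 1035 controls. From 3% to 15% it is roughly nominal (3.5% to 7.1% in the cases computed), and there the problem is an occasional conflict between tests within narrow bands of control rate. These sizes rest on the assumed alpha, control sizes and one count per woman.

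Severity is minor. These are secondary endpoints, and neither the discontinuation criteria (sections 9.3 and 9.4) nor the monitoring plan (section 10.5.4) uses the test.

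**What to change.** In section 10.5.3, replace the chi-square sentence. Make event counts with exact (Clopper-Pearson) 95% confidence intervals the main safety analysis, including the upper limit when no event occurs, and label the comparisons with historic rates descriptive. Where a test is kept, use Fisher's exact test against a control group, or an exact binomial test against a fixed literature rate. State alpha and sidedness, the abnormality cut-off and the source of each control rate. Count each woman once per comparison, since the laboratory panel is repeated at PK1, PK2 and V7.

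This changes wording only and needs no new data. The cost is conservatism. Fisher's actual size is 0.6% to 3.1% at rates of 1% to 10% with N = 1035. Against a 1% rate the exact binomial test needs two events in 10 (one event gives p = 0.096, two give 0.004). If the true rate were 10%, two or more events would occur only 26% of the time (1 − 0.9^10 − 10 × 0.1 × 0.9^9 = 0.264). A test this insensitive should not carry a safety conclusion, which is why the interval should lead. The interval's width at n = 10 is a matter of sample size, and no choice of test will narrow it.
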